1.3. Rationale for the Study

1.3.1. Rationale for the Use of ABI-009 in Advanced Malignant PEComas

The rationale behind mTOR inhibitor use in PEComas lies in the fact that both classic PEComas and PEComa-NOS have been shown to frequently harbor mutations in the *TSC1* and/or *TSC2* genes, which regulate cell proliferation via the mTOR pathway [58]. Tumors of the PEComa family are rare and usually occur sporadically. Lymphangioleiomyomatosis and AML also are seen at high frequency in patients with TSC, a disorder caused by mutation of *TSC1* or *TSC2*, for which the gene products negatively regulate mTORC1 through inhibition of the mTOR kinase activator, RHEB [58]. Both *TSC1* and *TSC2* gene products are involved in multiple cellular pathways, including regulation of cell proliferation, migration and differentiation through inhibition of the Rheb/mTOR/p70S6 kinase-signaling pathway [58]. Inactivation of the tuberin/hamartin complex in TSC thus leads to the activation of mTOR and the phosphorylation of p70S6K and ribosomal protein S6, and further promotes translational initiation and cell growth. This mTOR pathway is reported to be up regulated not only in TSC-associated AML, but also in sporadic AML or PEComas [59]. A high frequency of loss of heterozygosity (LOH) in *TSC2* gene is found in sporadic PEComas and sporadic classic renal and hepatic AMLs, with much lower LOH observed for *TSC1* [60]. In a recent study, activation of mTORC1 pathway, manifested by increased phosphorylated p70S6K and decreased phospho-Akt levels, was observed in 100% non-TSC AMLs and 93% of extra-renal PEComas [61].

Initial trials of these agents in the classic PEComas (AML, LAM) have led to a number of meaningful responses [4, 62], sparking interest in their use for advanced or recurrent PEComa-NOS. Clinical benefits have been observed in a number of PEComa case studies using rapamycin [5, 63], temsirolimus [64], and everolimus [65], although these responses have not been uniform. Wagner et al reported a short series of 3 patients treated with rapamycin for metastatic malignant PEComas. Radiographic responses were observed in all 3 patients. Loss of *TSC2* protein expression and evidence of baseline mTORC1 activation was found in all patients. Homozygous loss of *TSC1* was identified in one PEComa [5]. Dickson et al reported on the use of rapamycin in the treatment of 5 consecutive patients with extrarenal nonpulmonary PEComas with 3 CRs, 1 PR, and 1 case of progression [6]. In a retrospective study, the Royal Marsden Hospital reported that a population of 10 patients treated with either temsirolimus or rapamycin showed promising response rate but short remission duration [9]. It is

noteworthy that in a published clinical case, malignant PEComa tumors deemed inoperable or with borderline resectability achieved sufficient bulky tumor shrinkage with neoadjuvant rapamycin for a surgical resection. The option of neoadjuvant treatment may be considered for selected high-risk patients who can tolerate an mTOR inhibitor [63].

Additional justification for treating patients with malignant unresectable PEComa with ABI-009 instead of irradiation or doxorubicin-based chemotherapy: The available molecular and clinical evidence provides a strong rationale for using mTOR inhibitors in this disease. Thus participation in this clinical trial will be a reasonable option for many patients with advanced malignant PEComa. Most oncologists with expertise in sarcoma favor this approach since the disease is considered to be relatively insensitive to systemic chemotherapy and radiotherapy. Radiotherapy can be considered in selected cases, but may not be recommended depending on the location and/or extent of the tumor. Prior treatment with chemotherapy or radiotherapy would not exclude a patient from enrolling in the study and remain options at the discretion of the patient's treatment team.

The mechanisms of resistance to mTOR inhibition in malignant PEComa remain an important area for research [66, 67]. TFE3 gene rearrangement was recently reported in a small number of PEComas with no evidence of TSC2 mutation, which is suggested to cause resistance to mTOR inhibition, but this would need to be confirmed in a prospective study [68]. In addition, although rapamycin and rapalogs have shown some efficiency in the treatment of malignant PEComas, they induce AEs that can lead to treatment interruption, and thus compromising efficacy, and impact the quality of life, and lesions will typically regrow when the inhibitor is discontinued. More importantly, no formal clinical study has been conducted to investigate mTOR inhibitors safety and efficacy. These data clearly support the development of new mTOR inhibitors in an open study in the treatment of malignant PEComa.

It is estimated that 85% to 90% of the advanced malignant PEComas are metastatic and 10% to up to 15% are localized but unresectable. Allowing enrollment for both of these 2 subgroups of patients will permit assessing the efficacy of ABI-009 for response rate.

With favorable systemic safety at doses of 100 mg/m^2 given weekly IV observed in the phase 1 study, therapy with ABI-009 should result in manageable adverse events and provide significant therapeutic benefit to patients with malignant PEComas.

1.3.2. Rationale for the Schedule of Administration of ABI-009

A slightly different schedule of administration has been selected in the present study than was studied in the initial Phase 1 study CA401. In this study, 2 of 3 weekly schedule will be used instead of 3 of 4 weeks as in phase 1 clinical study CA-401.

The rationale for the modification to the schedule of administration of a dose of 100 mg/m^2 is to further improve the tolerance of ABI-009. As discussed in [Section 1.2.2.2](#), 19.4% of doses were missed at doses $\leq 100 \text{ mg/m}^2$. Most of the missing doses (83%) occurred at day 15, corresponding to the 3rd administration within a cycle. Thus, the

present study will examine 100mg/m² ABI-009 given weekly for 2 weeks followed by a week off. This change in schedule will not substantially impact the total drug received by the patients. In a period of 6 months (24 weeks) of treatment, the 2/3 schedule will allow 16 administrations, while the 3/4 schedule will allow 18 administrations.

2. STUDY OBJECTIVES AND ENDPOINTS

2.1. Objectives

2.1.1. Primary Objectives

To investigate the efficacy of the mTOR inhibitor ABI-009 in advanced malignant PEComa.

2.1.2. Secondary Objectives

The objectives are to further investigate the efficacy and safety of IV ABI-009 100 mg/m² given weekly for 2 of 3 weeks in patients with advanced malignant PEComa.

2.1.3. Exploratory Objectives

Exploratory Objectives

- To evaluate investigator assessed ORR
- To evaluate pharmacokinetic/pharmacodynamic relationships for safety and/or efficacy endpoints
- To evaluate tumor biomarkers:

2.2. Endpoints

2.2.1. Primary Endpoint

The primary endpoint is objective overall response rate (ORR), as determined by independent radiologic assessment using Response Evaluation Criteria in Solid Tumors (RECIST) v1.1.

2.2.2. Secondary Endpoints

The secondary endpoints are duration of response (DOR), progression-free survival (PFS) rate at 6 months, PFS, overall survival (OS), and safety/tolerability.

- DOR, PFS rate at 6 months, median PFS, and OS will be assessed separately in subgroups of patients with metastatic disease and locally advanced disease. Patients in the locally advanced tumor subgroup may be clinically indicated to receive surgery if there is sufficient tumor shrinkage, which could introduce a bias in the assessment of the DOR, PFS rate at 6 months, median PFS, and OS. Safety will be analyzed in all treated patients.

2.2.3. Exploratory Endpoints

- Investigator assessed ORR
- Pharmacokinetic/pharmacodynamic relationships for safety and/or efficacy endpoints

- To evaluate tumor biomarkers:
 - **Blood samples** will be obtained for cell-free plasma DNA collection (pretreatment, Cycle 4/Day 1, and post-treatment) for all patients.
 - Molecular analysis of cell-free plasma DNA assay using next-generation sequencing to assess the prevalence of mutations identified in the primary tumor sample over time as a measure of response to therapy.
 - **Tumor biopsy mutation analysis to assess resistance mechanisms.** Pre-treatment tumors (archival or fresh tissue biopsies) are required for all patients on this study to confirm diagnosis. This sample will also be used for baseline mutational analysis. In addition, an optional tumor biopsy will be collected for patients who provide additional consent at the end of treatment and/or if a patient experiences progression while on study.

3. OVERALL STUDY DESIGN

3.1. Study Design

This study is a prospective, single arm, phase 2, open label, multi-institutional study to determine the efficacy and safety profile of intravenous ABI-009 in patients with advanced malignant PEComa.

The study will be conducted in compliance with the International Council on Harmonisation (ICH) of Technical Requirements for Registration of Pharmaceuticals for Human Use/ GCP and applicable regulatory requirements.

This study will be conducted at approximately 9 sites in the United States.

3.2. Study Duration

The duration of enrollment for this study will last approximately 24 months. A cycle will consist of 3 weeks, with ABI-009 given weekly for 2 weeks followed by a week of rest. Treatment will continue until disease progression or unacceptable toxicity.

It is anticipated that each study patient will be on study for approximately 2 weeks of screening, approximately 6 months of treatment and 4 weeks of safety follow up. The total duration of the study is expected to be approximately 32 months.

3.3. End of Study, End of Treatment, End of Treatment Visit, Follow-up Period

End of Study (EOS) is defined as either the date of the last visit of the last patient to complete the study, or the date of receipt of the last data point from the last patient that is required for primary, secondary, and/or exploratory analysis, as pre-specified in the protocol.

End of Treatment (EOT) is defined as the date of the last dose of ABI-009 for an individual patient

End of Treatment Visit for a patient is when safety assessments and procedures are performed after the last treatment, which must occur at least 4 weeks (\pm 7 days) after the last dose of ABI-009.

Primary analysis for this study will occur after all patients have either completed the study or completed 6 months of treatment. Patients who are still active at the time of the primary analysis may continue on study until disease progression or medication intolerance is observed.

Primary Completion is the time when the last patient is assessed or receives an intervention for the purposes of final collection of data for the primary analysis.

Follow-up period is the on-study time period after the EOT Visit. All patients that discontinue study drug and have not withdrawn full consent to participate in the study will continue in the follow-up phase for survival and anticancer therapy. Follow-up will continue approximately every 12 weeks (+/- 3 weeks), or more frequently as needed,

until death, withdrawal of consent, or the study closes, whichever is the earliest. This evaluation may be made by record review and/or telephone contact.

The final patient's last visit for the study will be defined as whichever of the following represents the last time point:

- When the last patient on study has completed their Safety follow-up visit, or
- When the last patient on study has documented toxicities to ABI-009 and the toxicity has resolved, returned to baseline or is deemed irreversible after the Safety follow-up visit or
- When the last patient completes or discontinues the follow-up phase

4. STUDY POPULATION

4.1. Number of Patients

The anticipated enrollment into this study will be at least 30 evaluable patients. The rationale for the number of patients is detailed in [Section 10](#).

Investigators will be expected to maintain and submit every other week a screening log of all potential study candidates that includes limited information about the potential candidate, date, and outcome of the screening process (eg, enrolled into study, reason for ineligibility, or refused to participate).

Investigators will also be expected to document the reasons for which any patient enrolled on the trial with locally advanced malignant PEComa disease is not a suitable candidate for local treatment (eg, surgery or irradiation).

Before any study-specific procedure, the appropriate written informed consent must be obtained (see [Section 13.1](#)).

If for a given patient, the appropriate tumor tissue is not made available for centralized retrospective confirmation of malignant PEComa tumor type, this patient may be replaced. Additional patients may be enrolled if the Sponsor determines that the minimum required number of patients with evaluable tissue samples have not been enrolled.

4.2. Inclusion Criteria

A patient will be eligible for inclusion in this study only if all of the following criteria are met:

1. Patients must have a histologically confirmed diagnosis of malignant PEComa that is either metastatic or locally advanced and for which surgery is not a recommended option.
2. Patients must have available tumor block along with the corresponding pathology report (or approximately 30 unstained slides, with a minimum of 16 slides), and/or fresh biopsy to allow retrospective centralized confirmation of malignant PEComa and for mTOR pathway analysis and biomarker analysis.
3. Patients must have one or more measurable target lesions by CT scan or MRI. Measurable disease by RECIST v1.1.
4. Patients must not have been previously treated with an mTOR inhibitor.
5. Prior treatment (investigational or other), chemotherapy, radiotherapy, surgery, or other therapeutic agents (except mTOR inhibitors) is allowed, if completed after 5 half-lives or ≥ 28 days prior to enrollment, whichever is shorter.
6. Eligible patients, 18 years or older, with Eastern Cooperative Oncology Group (ECOG) performance status 0 or 1.

7. Patients must have the following blood chemistry levels at screening (obtained ≤ 14 days prior to enrollment (local laboratory):
 - a. total bilirubin $\leq 1.5 \times$ upper limit of normal (ULN) mg/dl
 - b. AST $\leq 2.5 \times$ ULN ($\leq 5 \times$ ULN if attributable to liver metastases)
 - c. serum creatinine $\leq 1.5 \times$ ULN
8. Adequate biological parameters as demonstrated by the following blood counts at screening (obtained ≤ 14 days prior to enrollment, local laboratory):
 - a. Absolute neutrophil count (ANC) $\geq 1.5 \times 10^9/L$;
 - b. Platelet count $\geq 100,000/mm^3$ ($100 \times 10^9/L$);
 - c. Hemoglobin ≥ 9 g/dL.
9. Serum triglyceride < 300 mg/dL; serum cholesterol < 350 mg/dL.
10. Male or non-pregnant and non-breast feeding female:
 - Females of child-bearing potential must agree to use effective contraception without interruption from 28 days prior to starting IP and while on study medication and have a negative serum pregnancy test (β -hCG) result at screening and agree to ongoing pregnancy testing during the course of the study, and after the end of study treatment. A second form of birth control is required even if she has had a tubal ligation.
 - Male patients must practice abstinence or agree to use a condom during sexual contact with a pregnant female or a female of childbearing potential while participating in the study. A second form of birth control is required even if he has undergone a successful vasectomy.
11. Life expectancy of > 3 months, as determined by the investigator.
12. Ability to understand and sign informed consent.
13. Willingness and ability to comply with scheduled visits, laboratory tests, and other study procedures.

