Patients will be evaluated for complete response (CR), partial response (PR), stable disease (SD), or progressive disease (PD) by CT imaging. Contrast enhanced MRI can also be used, as long as the same modality is used throughout the study. Baseline scan results can be accepted from outside institutions, but must be done within 4 weeks of starting therapy and must include (as clinically indicated), chest abdominal, and pelvic CT or MRI. The first response assessment by CT or MRI scans documenting target lesions will be done 6 weeks after first treatment and should be repeated every 6 weeks for the first year, then every 12 weeks thereafter until disease progression. If an initial observation of objective response (CR or PR) is made, a confirmation scan should be done at 6 weeks after initial observation. Scans should continue on schedule regardless of delays in ABI-009 dosing. The primary endpoint, ORR, will be determined by independent radiologist(s). The independent radiologic review will follow a separate imaging charter.

After disease progression, patients will be followed for survival every 12 weeks, or more frequently as needed, until death, withdrawal of consent, or the study closes, whichever is the earliest.

Overview of Key Safety Assessments

Safety and tolerability will be monitored through continuous reporting of treatment-emergent and treatment-related adverse events (AEs), AEs of special interest, laboratory abnormalities, and incidence of patients experiencing dose modifications, dose delay/dose not given, dose interruptions, and/or premature discontinuation of IP due to an AE. All AEs will be recorded by the investigator from the time the patient signs informed consent until 28 days after the last dose of IP. Adverse events will be graded by National Cancer Institute (NCI) Common Terminology Criteria for Adverse Events (CTCAE) v4.03.

Physical examination, vital sign, laboratory assessments (eg, serum chemistry, hematology), and ECOG performance status will be monitored. All SAEs (regardless of relationship to IP) will be followed until resolution. Laboratory analysis will be performed as per study schedule.

Statistical Considerations

Efficacy Analyses:

The primary analysis will address all study objectives and it will be conducted when all patients have had the opportunity to be treated for at least 6 months. All primary, secondary, and exploratory efficacy and safety analyses will be conducted at the time

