4.3. Exclusion Criteria

A patient will not be eligible for inclusion in this study if any of the following criteria apply:

1. Patients with lymphangioleiomyomatosis (LAM) are excluded.
2. Known active uncontrolled or symptomatic CNS metastases. A patient with controlled and asymptomatic CNS metastases may participate in this study. As such, the patient must have completed any prior treatment for CNS metastases ≥ 28 days (including radiotherapy and/or surgery) prior to start of treatment in this study and should not be receiving chronic corticosteroid therapy for the CNS metastases.
3. Active gastrointestinal bleeding.

4. Pre-existing thyroid abnormality is allowed provided thyroid function can be controlled with medication.
5. Uncontrolled serious medical or psychiatric illness. Patients with a “currently active” second malignancy other than non-melanoma skin cancers, carcinoma in situ of the cervix, resected incidental prostate cancer (staged pT2 with Gleason Score ≤6 and postoperative PSA <0.5 ng/mL), or other adequately treated carcinoma-in-situ are ineligible. Patients are not considered to have a “currently active” malignancy if they have completed therapy and are free of disease for ≥1 year).
6. Liver-directed therapy within 2 months of enrollment. Prior treatment with radiotherapy (including radio-labeled spheres and/or cyberknife, hepatic arterial embolization (with or without chemotherapy) or cyrotherapy/ablation) is allowed if these therapies did not affect the areas of measurable disease being used for this protocol.
7. Recent infection requiring systemic anti-infective treatment that was completed ≤14 days prior to enrollment (with the exception of uncomplicated urinary tract infection or upper respiratory tract infection).
8. Uncontrolled diabetes mellitus as defined by HbA1c >8% despite adequate therapy.
9. Unstable coronary artery disease or myocardial infarction during preceding 6 months.
10. Receiving any concomitant antitumor therapy.
11. Patients with history of interstitial lung disease and/or pneumonitis, or pulmonary hypertension.
12. Use of strong inhibitors and inducers of CYP3A4 within the 14 days prior to receiving the first dose of ABI-009. Additionally, use of any known CYP3A4 substrates with narrow therapeutic window (such as fentanyl, alfentanil, astemizole, cisapride, dihydroergotamine, pimozide, quinidine, terfanide) within the 14 days prior to receiving the first dose of ABI-009.

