- o. Screening CT/MRI scans must be performed within 28 days prior to study day 1, preferably as close to the day of enrollment as possible. Tumor evaluation by contrast-enhanced CT or MRI of the chest, abdomen, and pelvis will be performed during screening; every 6 weeks (\pm 3 days after C1D1 for the first year then every 12 weeks (\pm 7 days) thereafter until disease progression. EOT visit CT/MRI should be performed only for those patients that discontinue treatment for a reason other than disease progression per RECIST 1.1. If an initial observation of objective response (CR or PR) is made, a confirmation scan should be done at 6 weeks after initial observation.

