- Informed consent signed to collect for pre-treatment tumor sample (archived or fresh) along with pathology report for diagnosis confirmation and biomarker study for all patients
- Adverse event assessment
- Local Laboratory Assessments: chemistry, complete blood count (CBC), differential, platelet count, coagulation, urinalysis, thyroid function, pregnancy test (women of child-bearing potential, includes tubal ligations), HIV, hepatitis B surface antigen, hepatitis C antibody, fasting lipids
- Urinalysis (a urine dipstick may be used)
- CT or MRI, must be performed within 4 weeks prior to study day 1, preferably as close to the day of enrollment as possible

A patient is considered enrolled when the investigator decides that the patient has met all eligibility criteria. The investigator is to document this decision and date, in the patient's medical record and in/on the electronic case report form (eCRF).

All screening tests and procedures must be performed within 14 days of study day 1, unless specified otherwise in the study procedures listed in [Section 5](#). Once eligibility is confirmed, a site representative will complete and fax a patient eligibility criteria worksheet/tumor biopsy reference form to an AADI representative. The AADI representative will acknowledge receipt of the paperwork and confirm enrollment for that individual patient.

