6.2. Treatment Period

A patient is considered enrolled on study day 1 when the IP, ABI-009, is first administered. ABI-009 is to be administered after all other protocol-specified pre-dose assessments have been performed during each visit that it is required. Patients will continue therapy until disease progression or unacceptable adverse events.

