6.2.3. Response Assessment

Tumor response will be assessed by CT or MRI scan of the chest, abdomen, and pelvis; image preparation and evaluation will follow the specifications provided in the RECIST version 1.1. The same modality (CT or MRI) must be used at screening and throughout the study.

CT/MRI scans to be performed at the following frequency:

- ≤4 weeks prior to C1D1 (screening)

- followed by every 6 weeks after C1D1 for the first 1 year (\pm 3 days)
- followed by every 12 weeks (\pm 7 days) thereafter until disease progression. End of Treatment Visit CT/MRI should be performed only for those patients that discontinue treatment for a reason other than disease progression.

An unscheduled scan for suspected disease progression may be performed at any time. However, adherence to the planned imaging schedule is critical regardless of dose delays or unscheduled or missed assessments. Scans will be submitted to an independent central imaging laboratory for assessment by RECIST 1.1 and for determination of measurable disease. Determination of disease progression for clinical management of patients on study will be assessed at the local site. If an initial observation of objective response (CR or PR) is made, a confirmation scan should be done at 6 weeks after initial observation.

At the time of disease progression, if a biopsy is performed, a tumor sample will be collected and sent to the central laboratory, if available. Ensure that the surgical pathology report is submitted with the tumor tissue sample. Refer to the Instruction Sheet for tissue handling instructions for processing and shipping details.

Table 3: Analyte Listing

Chemistry	Hematology	Coagulation	Urinalysis	Other Labs
Sodium	WBC	PT	Specific gravity	Pregnancy test
Potassium	RBC	PTT	pH	ABI-009 PK (central)
Bicarbonate	Hemoglobin	INR	Blood	TSH, T3, T4
Chloride	Hematocrit		Protein	HIV
Total protein	MCV		Glucose	HBV sAg
Albumin	MCH		Ketones	HBV cAb
Calcium	MCHC		Microscopic	HCV Ab
Magnesium	RDW			Total Cholesterol
Phosphorus	Platelets			HDL
Glucose	Differential:			LDL
BUN	-Neutrophils			Triglyceride
Creatinine	-Lymphocytes			Biomarker development (central)
Total bilirubin	-Monocytes			
Alkaline phosphatase	-Eosinophils			
AST (SGOT)	-Basophils			
ALT (SGPT)				
Amylase				
Lipase				

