9.2. Prohibited Medications and Procedures

The use of certain medications, and illicit drugs within 5 half-lives or 28 days, whichever is shorter prior to the first dose of study drug and for the duration of the study will not be allowed. If a prohibited medication is required for single use (such as for a procedure) while study drug is held, the AADi medical monitor can approve such use.

The following medications or non-drug therapies are prohibited:

- Other anti-cancer therapy while on treatment in this study.
- Antiretroviral drugs (patients with known HIV are ineligible for study participation).
- Herbal remedies (eg, St. John's wort) unless approval is granted by the medical monitor.
- Rapamycin is metabolized primarily by CYP3A4. Drugs that are strong inhibitors or inducers of CYP3A4 may only be used under special circumstances (eg, as a single use for a procedure) while treatment with study drug is interrupted. The list may be modified based on emerging data.

- Use of any known CYP3A4 substrates with narrow therapeutic window (such as fentanyl, alfentanil, astemizole, cisapride, dihydroergotamine, pimozide, quinidine, terfanide) within the 14 days prior to receiving the first dose of ABI-009. Other medications may be allowed if there is agreement between the sponsor and investigator
- Use of strong inhibitors and inducers of CYP3A4 within the 14 days prior to receiving the first dose of ABI-009

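### The baseline scan can precede the end of prior systemic anticancer therapy, because the washout rule and the 28-day scan window are not tied together

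*Combined protocol and SAP*

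**What the plan says.** **Washout.** Inclusion criterion 5 (Section 4.2, repeated in the synopsis) covers earlier drugs, radiotherapy and surgery, other than mTOR inhibitors. Such treatment "is allowed, if completed after 5 half-lives or ≥ 28 days prior to enrollment, whichever is shorter". Section 9.2 uses the same shorter-of-two limit for prohibited medications but counts it from another date: "within 5 half-lives or 28 days, whichever is shorter prior to the first dose of study drug".

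**Baseline scan.** Table 2, footnote o: "Screening CT/MRI scans must be performed within 28 days prior to study day 1, preferably as close to the day of enrollment as possible". Section 6.2.3 gives the same four-week window before Cycle 1 Day 1. The synopsis (Overview of Key Efficacy Assessments) adds: "Baseline scan results can be accepted from outside institutions, but must be done within 4 weeks of starting therapy".

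**Enrollment.** Section 6.1: "A patient is considered enrolled when the investigator decides that the patient has met all eligibility criteria". Section 6.2: "A patient is considered enrolled on study day 1 when the IP, ABI-009, is first administered".

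**Related safeguards (Section 4.3).** Exclusion 6 bars liver-directed therapy within two months. It says that prior radiotherapy, embolization or ablation "is allowed if these therapies did not affect the areas of measurable disease being used for this protocol". Exclusion 2 sets a 28-day limit for treatment of CNS metastases, and exclusion 10 bars concurrent antitumor therapy.

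**Analysis.** Neither the efficacy set (Section 10.1.2) nor the ORR definition (Section 10.5.2) places a condition on when the baseline scan was taken relative to prior therapy. Section 10.5.2 refers to a separate imaging charter, which is not among the documents.

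**The concern.** The primary endpoint is confirmed response by RECIST 1.1, so it depends on tumor size at the baseline scan. If a patient is scanned, then receives further doses of another anticancer agent, stops, and starts ABI-009 a few days later, any shrinkage from those doses is measured from the trial's baseline. With a single arm, nothing in the data would separate it from an ABI-009 effect.

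A plain 28-day washout would prevent this: therapy would end on or before day -28, and a scan inside the 28-day window could not come before that. The half-life option removes the protection for agents that clear quickly. The exclusions do not restore it. Exclusion 6 concerns local treatments, exclusion 2 concerns CNS disease, and exclusion 10 concerns therapy still running. None reaches a systemic agent stopped between the scan and enrollment. The confirmation scan six weeks after a first response does not reset the baseline.

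**Working it through.** **1. The plan's own figures.** Section 10.2 gives, for 30 patients, a lower 95% limit of 14.7% at an observed ORR of 30% and a half-width of at most 18.7%. Section 10.5.1 specifies a two-sided exact binomial interval. The Clopper-Pearson limits for x responders out of n are

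- lower = the 0.025 quantile of Beta(x, n - x + 1)
- upper = the 0.975 quantile of Beta(x + 1, n - x)

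For x = 9 and n = 30 this gives 14.73% to 49.40%. The largest half-width over x = 0 to 30 is 18.70%, at 15/30. Both stated figures reproduce.

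**2. The overlap.** Inputs:

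- scan at the earliest permitted day, day -28 (Table 2 footnote o, Section 6.2.3)
- last prior dose at the latest permitted time, min(5 × half-life, 28) days before enrollment (criterion 5)
- L, the days from enrollment to day 1. Section 6.2 gives L = 0. Under Section 6.1 enrollment can come earlier; since that section also wants screening tests within 14 days of day 1 unless otherwise specified, L is taken as 0 to 14.
- half-life of the prior agent: not in the documents, so assumed over a range

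Maximum overlap in days = max(0, (28 - L) - min(5 × half-life, 28)).

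| Half-life (assumed) | 5 half-lives | Overlap, L = 0 | Overlap, L = 14 |
|---|---|---|---|
| 12 h | 2.5 d | 28 - 2.5 = 25.5 d | 14 - 2.5 = 11.5 d |
| 24 h | 5 d | 28 - 5 = 23 d | 14 - 5 = 9 d |
| 48 h | 10 d | 28 - 10 = 18 d | 14 - 10 = 4 d |
| 72 h | 15 d | 28 - 15 = 13 d | 0 d |

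The overlap vanishes when 5 × half-life reaches 28 - L: at 28/5 = 5.6 days for L = 0 and 14/5 = 2.8 days for L = 14. When the 28-day option governs, there is no overlap.

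**3. What a misattributed response would do to the estimate.** The documents give no rate, so the number k of such responses is an assumption. Take an observed 9/30 (30.0%, 14.7 to 49.4) and recount k responders as non-responders:

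- k = 1: 8/30 = 26.7% (12.3 to 45.9)
- k = 2: 7/30 = 23.3% (9.9 to 42.3)
- k = 3: 6/30 = 20.0% (7.7 to 38.6)

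Each such response is worth 1/30 = 3.3 percentage points.

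**The case against.** The best answer is that this will seldom happen. Section 1.1 reports no objective responses to cytotoxic drugs in metastatic PEComa, and criterion 4 excludes prior mTOR inhibitors, the class for which the protocol does cite responses. To be miscounted, a patient would need shrinkage that reaches the response threshold and persists to a confirmation scan six weeks later. The overlaps above are extremes, the protocol prefers a scan close to enrollment, and the imaging charter may already hold a baseline rule.

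Most of this stands, and it limits the size of the problem. It does not remove it. A preference is not a requirement. Criterion 5 admits investigational agents of unknown activity, and the title of reference 12, cited for the statement on cytotoxic drugs, describes a colonic PEComa responsive to doxorubicin and ifosfamide. The charter could not be checked, and sites time the scan from the protocol.

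A reader might go further in three directions that the documents do not support:

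- **Irradiation or resection credited to ABI-009.** Exclusion 6 requires that prior radiotherapy did not affect the measurable disease used in the trial. Neither surgery nor radiotherapy has a half-life, so both fall naturally under the 28-day option, where there is no overlap. The criterion could say so more clearly, but that is a matter of wording.
- **False early progression.** Growth between the scan and day 1 can occur with any scan window, whatever the washout. It does not come from this gap.
- **A wrong 14.7%.** That limit is conditional on an observed 30% and is correct. The recount above shows sensitivity to misattribution; it does not correct the plan's figure.

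**Conclusion.** The point holds for prior systemic agents only. The protocol as written allows the baseline scan to precede the last dose of such an agent if its half-life is below about 5.6 days (enrollment on day 1) or 2.8 days (enrollment 14 days before day 1). The gap therefore exists under both definitions of enrollment, although its length depends on which applies. At the assumed half-lives it is at most 25.5 days in the first case and 11.5 days in the second.

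The text of the protocol is clear on this. What is uncertain is how often it would alter a response: no document gives a rate, the protocol's own account of chemotherapy in PEComa suggests rarely, and the imaging charter was not available. The 3.3 points of ORR per patient are an illustration, not an estimate of bias. Because the effect would favor the drug in an uncontrolled primary endpoint and is easily prevented, closing the gap is a cheap improvement.

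**What to change.** Add one sentence to Table 2 footnote o, Section 6.2.3 and the synopsis: *For patients who received prior systemic anticancer therapy, the baseline scan, including an outside scan, must be obtained after the last dose of that therapy.* Check that the imaging charter says the same, and add a line to the eligibility worksheet. Section 9.1 already has all prior cancer therapies recorded in the eCRF, so compliance should be easy to verify.

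The rule works under either definition of enrollment, but Sections 6.1 and 6.2, and the different starting points for the washout in Sections 4.2 and 9.2, should be reconciled in the same amendment. No change to the washout length is proposed. Limiting the sentence to systemic therapy avoids repeat scans after radiotherapy that spared the measurable lesions, which exclusion 6 permits.

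The cost is that a few patients, mainly those with an early outside scan, will need the screening scan taken later or repeated.
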